2. STUDY OBJECTIVES, ENDPOINTS AND HYPOTHESES

2.1. Objectives

Primary Objective:

The primary objective of this study is to estimate the incidence rate (percentage) of eyes with clinically significant slit-lamp findings (Grade 3 or 4) related to each study lens (Test lens and Control lens) after approximately 2-weeks of lens wear.

Exploratory Objectives:

The exploratory objectives of this study include the estimation of the mean difference between study lenses (Test lens and Control lens) with respect to distance monocular high luminance, high contrast (HLHC), logMAR visual acuity (at the 1-week follow-up visit), and CLUE comfort, vision, and handling scores (at the fitting, 1- and 2-week follow-up visits). Additional exploratory objectives of the study are to estimate the mean and standard deviation of the settled toric roation of each study lens (Test lens and Control lens) following lens settling and after 1- and 2-weeks of lens wear, and to assess the toric lens orientation of each study lens, 1- and 3-minutes after lens insertion. Adverse events will also be monitored and collected.

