2.2. Endpoints

Primary endpoint:

1. Percentage of Eyes with slit-lamp findings (Grade 3 or 4) related to study lens wear

Slit Lamp Findings (Grade 3 or higher) will be assessed for each subject eye at all study visits (scheduled and unscheduled). However, the primary endpoint will be the percentage of eyes with Grade 3 or higher SLFs related to study lens wear, after approximately 2 weeks of lens wear.

SLFs will be evaluated and classified using the FDA Grading scale rating from 0 to 4, where Grade 0 represents the absence of findings and 1 to 4 representing successively worse findings (i.e., Grade 1=trace, Grade 2= mild, Grade 3=moderate and Grade 4= severe).

Exploratory Endpoints:

1. Distance Monocular HLHC logMAR Visual Acuity

Visual acuity (VA) will be assessed monocularly at the 1-week follow-up visits under high-luminance high contrast (HLHC) conditions at a test distance of 4 meters using ETDRS Charts. The logMAR VA score is a continuous endpoint.

2. CLUE Comfort Scores

Subjective comfort will be assessed using the Contact Lens User Experience (CLUE) questionnaire. CLUE will be assessed at the fitting, 1- and 2-week follow-up visits. The CLUE comfort score is a conintuous endpoint.

CLUE is a validated patient-reported outcomes questionnaire to assess patient-experience attributes of soft, disposable contact lenses (comfort, vision, handling, and packaging) in a contact-lens wearing population in the US, ages 18-65. Derived CLUETM scores using Item Response Theory (IRT) follow a normal distribution with a population average score of 60 (SD 20), where higher scores indicate a more favorable/positive response with a range of 0-120. A 5-point increase in an average CLUETM score translates into 10% shift in the distribution of scores for population of soft contact lens wearers.⁵

- 3. CLUE Vision Scores at the fitting, 1-, and 2-week follow-up visits. The CLUE vision score is a conintuous endpoint.
- 4. CLUE Handling Scores at the fitting, 1-, and 2-week follow-up visits. The CLUE handling score is a conintuous endpoint.

CR-6553, v3.0 JJVC CONFIDENTIAL

5. Toric Lens Orientation

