5. TEST ARTICLE ALLOCATION AND MASKING

5.1. Test Article Allocation

The study lenses will be worn bilaterally in a randomized fashion using a 2×2 crossover design with 2 lens types and 2 periods.

A computer-generated randomization scheme will be used to randomly assign subjects to one of two unique sequences of lens wear. The randomization scheme will be provided by an internal independent unmasked Biostatistician who is independent of the study team and not involved in the study conduct or analyses, beyond the randomization codes and schedule generation. The randomization scheme will be generated using the PROC PLAN procedure from Statistical Analysis System (SAS) Software Version 9.4 or higher (SAS Institute, Cary, NC).

The assignment of subjects will be performed at the first visit prior to the first fitting. Clinical sites must follow the randomization scheme provided. The following must have occurred prior to randomization:

- Informed consent must have been obtained
- The subject must have met all inclusion and exclusion criteria
- The subject history and baseline information must have been collected

When dispensing test articles, the following steps should be followed to maintain randomization codes:

- 1. Investigator or designee (documented on the Delegation Log) will consult the randomization scheme (lens fitting schedule) to obtain the test article assignment for that subject prior to dispensing.
- 2. Investigator or designee will record the subject's number on the appropriate line of the randomization scheme (lens fitting schedule).
- 3. Investigator or designee will pull the appropriate test articles from the study supply. All test articles that are opened, whether dispensed (placed/fit on eye or dispensed outside the clinical site) or not, must be recorded on the Test Article Accountability Log in the "Dispensed" section.

CR-6553, v3.0 JJVC CONFIDENTIAL

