1.30.	Schedule next visit	Schedule the next visit to occur in 7(±2) days (counting the day of this visit as day 0, the subject may return on day 5 through 9). Ensure the subject is instructed to wear the study lenses for at least 1 hour immediately prior to attending the next visit.			

VISIT 2

Visit 2 will occur 5 to 9 days following Visit 1. Subjects must present to this visit wearing the study lenses in both eyes, and lenses must have been worn for at least 1 hour prior to the visit.

		Visit 2: Follow-Up #	1			
Step	Procedure	Details				
2.1.	Wear time and compliance	Record the subjects wearing time and comfortable wearing time. Subjects must have worn lenses for at least 8 hours on at least 5 days between the dispensing visit and this visit, and for at least 1 hour prior to attending this visit.				
2.2.	Review medical history and concomitant medications	Record any changes to the (including adverse events medications.				
2.3.	Subject reported ocular symptoms	Record any subject repor response to a verbal oper questionnaire.				
2.4.	Follow-up PRO questionnaire	Subjects will complete a PRO questionnaire to assess their experience with the study lenses. The glare PRO questionnaire will be completed first, followed by the CLUE questionnaire, followed by the other PRO items.				
2.5.	Entrance visual acuity	Record the entrance Snel wearing the study lenses.		ch eye while		
2.6.	Distance ETDRS visual acuity	Measure monocular discontrast (HLHC) visual 4 meters. Measure each eye using below:	acuity using E	TDRS charts	at	
		Condition	HI	HC		
		Room illumination	> 40	0 lux		
		Chart luminance	120 - 20	00 cd/m ²		
		Eye	OD	os		
		Charts	HC-1	HC-2		
2.7.	Toric lens orientation	Recorded letter-by-letter results into EDC. Record the toric lens orientation for each eye to the nearest degree.				
2.8.	Lens removal	Remove and place both lenses into a lens case with saline solution. Do not discard the lenses.				

Visit 2: Follow-Up #1			
Step	Procedure	Details	
2.9.	Biomicroscopy	The FDA Slit Lamp Classification Scale will be used to grade findings. If any slit lamp finding is graded as 3 or worse, the subject must be discontinued, an adverse event will be recorded, and the subject will be monitored as per the guidelines given in section Error! Reference source not found Should the clearance of the fluorescein need to be expedited, preservative-free rewetting drops or artificial tears may be instilled.	

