14.2. Sample Size Justification

This study was not designed or powered to test any statistical hypotheses with respect to incidence (percentage) of study lens-related grade 3 or higher SLFs after approximately 2-weeks of lens wear. Instead, the sample size and study design were based on clinical considerations and operational feasibility. A sample size of 60 subjects (120 eyes) to complete (through Visit 6), will provide adequate precision around the estimate of the percentage of eyes with study lens related grade 3 or higher SLFs as measured by the half-width of a 95% CI. Percision estimates were provided using difference scenarios for the percentage of events and are displayed in Table 7 below.

Table 7: Half-Width of the 95% Confidence Intervals for Proportion of Eyes with Grade 3+ SLFs

Sample Size (number of subject to complete)	Proportion of Grade 3 + SLFs	Confidence Interval Half-Width	Estimated Upper Limit
60 (120 eyes)	0 (no events)	0.02466	0.02466
	0.0083 (1 event)	0.03057	0.03887
	0.0167 (2 events)	0.03488	0.05158

A total of 60 subjects are targeted to complete the study. To account for subject drop-out approximately 66 (based on a drop-out rate of 10%) subjects will be enrolled in this study to ensure that at least 60 subject complete the study.

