14.5. Primary Analysis

The summary of the primary endpoint will be conducted on the safety population.

The distribution of eyes (n, %) with SLF grade level will be summarized by study lens type. The grading SLFs scale is from 0 to 4, where Grade 0 represents the absence of findings and 1 to 4 representing successively worse findings (i.e., Grade 1 = trace, Grade 2 = Mild, Grade 3 = moderate and Grade 4 = severe).

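### Table 7 (14.2) presents one-sided 95% exact limits on 120 eyes treated as independent as half-widths of 95% CIs, and 14.5 plans no interval for the primary percentage

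*Combined protocol and SAP*

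**What the plan says.** Section 2.1 makes the primary objective one of estimation: "The primary objective of this study is to estimate the incidence rate (percentage) of eyes with clinically significant slit-lamp findings". Section 2.2 fixes the eye as the unit: "the primary endpoint will be the percentage of eyes with Grade 3 or higher SLFs related to study lens wear", taken after about two weeks of wear.

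Section 14.2 claims: "A sample size of 60 subjects (120 eyes) to complete (through Visit 6), will provide adequate precision around the estimate of the percentage". It measures that precision by the half-width of a 95% CI and refers to Table 7, titled "Half-Width of the 95% Confidence Intervals for Proportion of Eyes with Grade 3+ SLFs". The table gives a half-width and an upper limit for 0, 1 and 2 events. It does not state the interval method, the sidedness, or any allowance for two eyes per subject. The same section says that "the sample size and study design were based on clinical considerations and operational feasibility".

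On allocation, section 5.1 says: "The study lenses will be worn bilaterally in a randomized fashion using a 2×2 crossover design with 2 lens types and 2 periods". Each subject therefore contributes two eyes on the same lens in each period.

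For the primary analysis, section 14.5 says: "The distribution of eyes (n, %) with SLF grade level will be summarized by study lens type". Section 14.1 adds only counts and percentages for categorical data. Section 14.7 plans two-sided 95% CIs for the exploratory visual acuity, CLUE and settled-orientation endpoints.

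**The concern.** There are two linked defects.

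First, the figures behind the precision statement are not what their title says. A reader who sees half-widths of 95% CIs in 14.2, and two-sided 95% CIs in 14.7, will take Table 7 as two-sided. The table also counts 120 eyes as 120 independent observations, although fellow eyes share the subject, the lens type and the wear period.

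Second, the study exists to estimate a percentage, and 14.2 describes the precision of an interval for it, but 14.5 never plans that interval. The absence of hypothesis testing does not explain this, because the exploratory endpoints receive CIs under the same statement. With the 0 to 2 events that Table 7 considers, the upper limit carries most of the information in the result.

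What is at stake is how precision is described at planning and how the primary result is reported.

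**Working it through.** **Inputs.** From 14.2: 60 completing subjects, 120 eyes, printed proportions 0, 0.0083 and 0.0167. From 5.1: both eyes wear the same lens in each period. The documents give no inter-eye correlation (ICC), so 0 to 1 is used as an assumed range.

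**Step 1: reproduce Table 7.** The one-sided 95% exact (Clopper-Pearson) upper limit is U = BetaInv(0.95; x + 1, n − x) with n = 120. Taking x as 120 times the printed rounded proportion gives x = 0, 0.996 and 2.004.

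| Events | U | U − p | Printed upper limit | Printed half-width |
|---|---|---|---|---|
| 0 | 0.02466 | 0.02466 | 0.02466 | 0.02466 |
| 1 | 0.03887 | 0.03057 | 0.03887 | 0.03057 |
| 2 | 0.05158 | 0.03488 | 0.05158 | 0.03488 |

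All six entries match. Whole counts of 1 and 2 give 0.03892 and 0.05153, so the small differences come from rounding the proportions. The two-sided exact, Wald and Wilson intervals, and half of the 90% exact interval, do not reproduce the table.

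**Step 2: what the title describes.** Two-sided 95% exact intervals on 120 independent eyes:

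| Events | Lower | Upper | Half the width | Printed half-width |
|---|---|---|---|---|
| 0 | 0 | 0.0303 | 0.0151 | 0.02466 |
| 1 | 0.0002 | 0.0456 | 0.0227 | 0.03057 |
| 2 | 0.0020 | 0.0589 | 0.0284 | 0.03488 |

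The printed half-widths are too large for a two-sided 95% CI, and the printed upper limits are too small.

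**Step 3: two eyes per subject, zero events.** With eye rate p and inter-eye correlation ICC, the chance that neither eye of a subject is affected is (1 − p)² + ICC·p(1 − p). The upper limit solves [(1 − p)² + ICC·p(1 − p)]^60 = α, with α = 0.05 for the one-sided limit and 0.025 for the upper end of a two-sided CI.

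| Assumed ICC | One-sided 95% | Upper end of two-sided 95% |
|---|---|---|
| 0 | 2.47% | 3.03% |
| 0.25 | 2.82% | 3.46% |
| 0.5 | 3.28% | 4.03% |
| 0.75 | 3.93% | 4.82% |
| 1 | 4.87% | 5.96% |

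The step from 2.47% to 3.03% is sidedness; movement down a column is clustering. The cruder design-effect approach, with effective n = 120/(1 + ICC) = 96 and 80, gives one-sided limits of 3.07% and 3.68% at ICC 0.25 and 0.5, and agrees with the exact model at 0 and 1. Negative correlation hardly helps: if no bilateral cases can occur, (1 − 2p)^60 = 0.05 gives 2.44%.

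**Step 4: a limit that needs no ICC.** The eye rate cannot exceed the rate of subjects with at least one affected eye. An exact upper limit for the subject rate is therefore a valid upper bound for the eye rate at any correlation. For 0, 1 and 2 of 60 subjects, the one-sided 95% limits are 4.87%, 7.66% and 10.12%, and the two-sided 95% upper limits are 5.96%, 8.94% and 11.53%.

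The subject-level lower limit is not a bound for the eye rate. Eleven unilateral cases give an eye rate of 11/120 = 9.17%, below the two-sided lower limit of 9.52% for 11/60.

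**The case against.** **Nothing depends on Table 7.** Section 14.2 bases the sample size on clinical and operational grounds, and sections 2.3 and 14.4 exclude hypothesis testing. This stands. A reader might infer that 60 subjects are too few or that a claim fails. The documents set no precision target, margin or threshold, so that inference has no support.

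**The two errors partly offset each other.** A reader might infer that Table 7 shows the best case throughout. That holds only for the upper-limit column. On the metric that 14.2 names, the printed zero-event half-width of 2.466% exceeds half of the two-sided interval until the ICC reaches about 0.78: the limit would have to be 2 × 2.466% = 4.93%, and the pair model with α = 0.025 then gives ICC ≈ 0.78. This objection stands.

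**Affected subjects can be found anyway.** A reader might infer that the eye counts hide how many subjects were affected. Section 7.2 says "If any slit lamp finding is graded as 3 or worse, the subject must be discontinued" and requires an adverse event to be recorded. Section 13.3 requires separate forms for each eye when an event is bilateral, and 14.7 lists every event with treatment and relatedness. Affected subjects are therefore largely recoverable. However, slit-lamp grade is not a named field of that listing, and a listing is not a planned interval.

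**A subject-level CI is not an interval for the eye percentage.** This is true, and the bound is loose when findings are unilateral. A cluster-adjusted eye-level interval is a legitimate alternative, but it needs a correlation that cannot be estimated from zero events and is barely estimable from one or two. The subject-level exact limit does not depend on it.

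**Conclusion.** The point holds as a labelling and reporting defect. It is certain that Table 7 contains one-sided 95% exact limits on 120 independent eyes (and those limits minus the proportion), that its title describes something else, and that 14.5 plans no interval for the primary percentage. Relative to a two-sided 95% CI on independent eyes, the zero-event half-width is printed as 0.02466 where 0.0151 would be correct, and the upper limit as 0.02466 where 0.0303 would be correct.

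The size of the clustering effect is less certain because it depends on assumed ICCs. The general statement is that any positive correlation raises the upper limits, with 4.87% one-sided or 5.96% two-sided as the ceiling at zero events in 60 subjects. These figures assume exactly 60 subjects with data on a lens; 14.5 uses the safety population, so actual denominators may differ.

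The endpoint definition in 2.2 is not in question, and no sample size, threshold or decision rule changes.

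**What to change.** 1. **Section 14.2, Table 7.** Either relabel the entries as one-sided 95% exact upper limits assuming independent eyes (and the other column as limit minus proportion), or replace them with two-sided 95% values. Replacement would match 14.7 and the interval proposed below for 14.5. In either case add the 60-subject limits from step 4 as a conservative bound, with the same sidedness as the rest of the table.

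2. **Section 14.5.** Add text such as: *For each lens, the number and percentage of eyes with a lens-related Grade 3 or higher SLF will be reported. The number and percentage of subjects with at least one such eye will also be reported, with a two-sided 95% exact (Clopper-Pearson) CI. The upper limit of that CI, but not its lower limit, will serve as a conservative bound for the eye percentage that does not depend on the inter-eye correlation.*

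The cost is wording in two sections and one extra line per lens in the primary table, with no additional subjects or data. The downside is that the quoted limits are less favourable, and the bound is conservative when findings are unilateral: one such case gives 7.66% (1 of 60 subjects) against 3.89% (1 of 120 independent eyes), both one-sided.

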14.6. Secondary Analysis

Not applicable.

14.7. Exploratory Analyses

Summary for exploratory endpoints will be provided for both the ITT and the Per-Protocol populations. However, all analyses for exploratory endpoints will be conducted on the ITT population.

Distance Monocular HLHC logMAR visual acuity

Distance monocular HLHC logMAR visual acuity at the 1-week follow-up will be summaried and presented only descriptively by lens type accompanied with the 2-sided 95% CIs. Summary statistics are described in section 14.1.

CLUE Comfort, Vision, and Handling Scores

The analysis of exploratory endpoints of CLUE comfort, vision and handling at the fitting, 1-, and 2-week follow-up visits will be conducted separately for each CLUE domain. The exploratory analysis of each CLUE score endpoints will include the estimation of mean CLUE scores and associated 95% CIs for each study lens (Test lens and Control lens). Additionally, the mean difference between the Test and Control lens paired with the 95% CI will be calculated.

CLUE scores will be analyzed using a linear mixed model, adjusting for baseline scores as a covariate. Sequence of lens wear, study period, lens type (Test and Control), timepoint (fitting, 1-week, and 2-week follow-up visit), and the ineraction lens type by timepoint will be included as fixed effects. Other baseline characteristics such age, gender, and/or race will be included as fixed covariates when appropriate. Site and subject nested within site will be included as random effects (G-side). Residual errors from measurements within the same subject and timepoint across study period will be modeled using an unstructured covariance structure (UN). If the model does not converge, other covariance structures will be considered. The Kenward and Roger method will be used for the denominator degree of freedom. Estimates for each study lens and between study lenses (Test lens and Control lens) will be carried out using two-sided 95% CIs for the least-square mean and/or mean difference.

Toric Lens Orientation

The distribution (counts, percentages) of eyes for the toric Orientation (in degrees) at 1- and 3-minutes after lens insertion will be summarized by timepoint (fitting, 1-, and 2-week follow-up) and lens type.

Mean Settled Lens Orientation

Mean settled lens orientation will be summarized separately for each timepoint (fitting, 1-, and 2-week follow-up visits) and lens type (Test and Control). Mean settled lens orientation is calculated by eye by averaging across all lens orientation measurements collected at least 15-minutes after lens insertion. The standard deviation of average settled lens orientation will also be calculated.

The exploratory analysis of this exploratory endpoint will include the estimation of the mean settled rotation by study lens paired with the corresponding two-sided 95% CIs for each lens, and the point estimate with the two-sided 95% CI for the mean difference.

Mean settled rotation will be analyzed using a linear mixed model. Sequence of lens wear, period, lens type, and first order carryover effect will be included in the model as fixed effects. Other baseline characteristics may be included, such as, race and age. Subject will be included as a random effect. Residual errors between measurements within a subject across periods will be modeled using an unstructured (UN) covariance structure. The Kenward and Roger Method will be used for the calculation of denominator degrees of freedom. Estimates will be calculated using two-sided 95% confidence intervals constructed for the least-square mean and/or least-square mean difference.

Adverse Events

All Adverse Events reported during this study will be provided in a listing. This listing will include subject demographic information, treatment information (associated with the time of the reported AE), AE type (ocular or non-ocular), seriousness / classification, causality or relatedness, adverse event severity, outcome, actions taken and the associated start and end date / time for each AE.

Additional exploratory analyses may be considered at the discretion of the study sponsor.

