Investigational Product (Test lens): The test product will be rotationally stabilized astigmatic soft contact lenses in senofilcon A with a chromophore to filter High-Energy Visible Light (HEVL). Approved Product (Control lens): The control product will be DAILIES TOTAL1® for Astigmatism Contact Lenses (DT1fA).		
Wear Schedule: Daily wear		
Replacement Schedule: Daily disposable		
Primary Objective: The primary objective of this study is to estimate the incidence rate (percentage) of eyes with clinically significant slit-lamp findings (Grade 3 or 4) related to each study lens (Test lens and Control lens) after approximately 2-weeks of lens wear.		
Exploratory Objectives: The exploratory objectives of this study include the estimation of the mean difference between study lenses (Test lens and Control lens) with respect to distance monocular high luminance, high contrast (HLHC), logMAR visual acuity (at the 1-week follow-up visit), and CLUE comfort, vision, and handling scores (at the fitting, 1- and 2-week follow-up visits). Additional exploratory objectives of the study are to estimate the mean and standard deviation of the mean settled toric orientation of each study lens (Test lens and Control lens) following lens settling and after 1- and 2-weeks of lens wear, and to assess the toric lens orientation of each study lens, 1- and 3-minutes after lens insertion. Adverse events will also be monitored and collected.		
Primary endpoint: • Indicidence (percentage) of eyes with Grade 3 or 4 slit lamp findings related to the study lenses (Test lens and Control lens) after 2-week of lens wear. Exploratory endpoints: • Distance Monocular HLHC logMAR at 4m at the 1-week follow-up visit • Contact Lens User Experience (CLUE) comfort scores at the fitting, 1-, and 2-week follow-up visits • CLUE vision scores at the fitting, 1-, and 2-week follow-up visits • CLUE handling scores at the fitting, 1-, and 2-week follow-up visits • Lens orientation at 1 minute and 3 minutes following insertion at fitting • Mean Settled Lens Orientation at the fitting, 1-, and 2-week follow-up visits		

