14. STATISTICAL METHODS

14.1. General Considerations

Statistical Analysis will be undertaken by the sponsor or under the authority of the sponsor. A general description of the statistical methods to be implemented in this clinical trial is outlined below.

Descriptive statistics will be reported for all key variables as appropriate. Continuous data will be summarized descriptively by sample size (n), mean, standard deviation (SD), median, minimum (Min) and maximum (Max). Categorical data will be summarized descriptively by frequency count (n) and percentage (%) of subjects or eyes within each category level. Summary tables will be presented by event (Baseline, Fitting, 1-week follow-up, 2-week follow-up, Unscheduled and Final Evaluations) and study lens type (Test and Control) as applicable, for the analysis set of interest. The denominator for all percentages will be the number of subjects (or eyes as applicable) with available data in the lens group under consideration. Unscheduled visits and tele-visits will be summarized separately and will be excluded from the primary and secondary analysis.

All available data collected at scheduled visits will be used in the statistical summaries and analyses, with no imputation of missing data. Unscheduled visits will be summarized separately and will be excluded from the statistical analysis. All data summaries and statistical analyses will be performed using the SAS software Version 9.4 or higher (SAS Institute, Cary, NC).

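### The Test–Control difference in 1-week visual acuity is an exploratory objective, but the plan gives no confidence interval or period-adjusted estimate for it

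*Combined protocol and SAP*

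**What the plan says.** One exploratory objective in section 2.1, set for the first-week visit, is to estimate this quantity: "mean difference between study lenses (Test lens and Control lens) with respect to distance monocular high luminance, high contrast (HLHC), logMAR visual acuity". The CLUE comfort, vision and handling scores are named in the same sentence. The synopsis repeats it: "The exploratory objectives of this study include the estimation of the mean difference between study lenses (Test lens and Control lens").

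Section 14.7 then states that 1-week acuity "will be summaried and presented only descriptively by lens type accompanied with the 2-sided 95% CIs", and refers to section 14.1 for the summary statistics. Section 14.1 lists n, mean, SD, median, minimum and maximum, tabulated by event and lens type.

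For the other continuous endpoints section 14.7 goes further. For CLUE, "the mean difference between the Test and Control lens paired with the 95% CI will be calculated", from a linear mixed model that includes sequence, period and lens type. For mean settled orientation it plans "the point estimate with the two-sided 95% CI for the mean difference", also from a mixed model with sequence and period.

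**The concern.** The objective names a contrast and the analysis section does not produce it. Restricting the presentation to description by lens type rules out reading the planned intervals as intervals for the difference.

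The choice of design sharpens the point. Section 4.2 justifies the 2×2 crossover on the ground that subjects serve as their own controls. For acuity that pairing would go unused. The report would carry two separate means with separate intervals, and a reader wanting the precision of the difference could only combine them as if they came from independent groups, which they do not.

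**Working it through.** The plan states no SD, correlation or precision target for acuity, so there is no figure to reproduce. The finding rests on comparing the texts; the arithmetic only illustrates the consequence.

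**Objective against analysis**

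| Endpoint | Objective (synopsis, 2.1) | Analysis (14.7) |
|---|---|---|
| HLHC acuity, 1 week | Test–Control mean difference | Per-lens summaries with 95% CIs; no difference, no model |
| CLUE comfort, vision, handling | Test–Control mean difference | Mixed model; difference with 95% CI |
| Mean settled orientation | Mean and SD per lens | Mixed model; difference with 95% CI |

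Acuity is the only endpoint named in the mean-difference objective that has no planned difference.

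**Can the interval be recovered from the per-lens results?**

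Inputs: n = 60 completers (section 14.2). Assumed: SD = 0.10 logMAR for a subject's two-eye mean, equal for both lenses; between-lens correlation r from 0 to 0.9; all 60 subjects contribute to both periods.

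- Per lens: half-width = t(0.975, 59) × SD/√n = 2.001 × 0.10/√60 = 0.026.
- Difference: half-width = t(0.975, 58) × SD × √(2(1−r)/n) = 2.002 × 0.10 × √(2(1−r)/60).

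| r | 0 | 0.3 | 0.5 | 0.7 | 0.9 |
|---|---|---|---|---|---|
| Half-width of the difference | 0.037 | 0.031 | 0.026 | 0.020 | 0.012 |

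The per-lens half-width is 0.026 in every column, while the half-width of the difference varies about threefold. The per-lens output does not show which column applies. Across SDs of 0.06 to 0.12, the per-lens half-width runs from 0.016 to 0.031 and that of the difference from 0.007 to 0.044.

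**Combining the two intervals as independent**

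The variance used would be 2·SD²/n, against the paired 2·SD²(1−r)/n. The width ratio is 1/√(1−r): 1.195 at r = 0.3, 1.414 at 0.5 and 1.826 at 0.7.

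**Period effect in the subtracted means**

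With n1 and n2 completers in the two sequences, the raw difference carries |n1−n2|/(n1+n2) of any period effect. For assumed splits:

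- 30/30: 0
- 31/29: 2/60 = 3.3%
- 33/27: 6/60 = 10%

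**A separate gap: two eyes per subject**

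Acuity is measured in each eye, and section 14.7 does not say how the eyes enter the per-lens intervals. Let ICC be the inter-eye correlation (assumed). If the eyes were treated as independent, per-lens coverage would be 2Φ(1.96/√(1+ICC)) − 1: 0.914, 0.890 and 0.856 for ICC 0.3, 0.5 and 0.8. The width ratio above would become 1/√((1+ICC)(1−r)), which runs from 0.89 (ICC 0.8, r = 0.3) to 1.60 (ICC 0.3, r = 0.7). The combined interval could then be too narrow or too wide. The plan does not say that eyes will be treated this way.

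**The case against.** The strongest reply is that the descriptive treatment looks deliberate. Section 14.7 writes out full models for CLUE and settled orientation, so the authors apparently chose not to model acuity, and the objective may be the loosely worded side. Settled orientation shows the opposite mismatch: its analysis delivers more than its objective asks. This stands as a reason to let the sponsor choose which text to change. It does not reconcile the two texts.

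A second reply is that the objective asks only for estimation of a mean difference and mentions neither an interval nor period adjustment, and that subtraction gives a point estimate. That is correct as far as it goes. However, the plan does not say that the subtracted difference will be reported, and an estimate without its precision falls short of what the plan provides for CLUE under the same objective and the same no-testing rule (sections 2.3 and 14.4).

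Third, the width ratios depend on assumed correlations and on a reader combining the intervals wrongly, which the plan does not propose. The 33/27 split is near the extreme: from 33 randomized per sequence, it needs all six losses in one sequence. Both points are fair, and the figures are illustrative only.

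The closing sentence of section 14.7, allowing further exploratory analyses at the sponsor's discretion, does not pre-specify this one. Section 14.10 commits the study to the analyses as written and requires any change to be documented and justified in the report.

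**Conclusion.** The concern holds. The documents set out to estimate a Test–Control difference in 1-week acuity and then plan an analysis that gives no interval for it, no period adjustment and no use of the pairing. This conclusion needs no assumed value.

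The size of the consequence cannot be fixed from the documents, because it depends on a between-lens correlation they do not give. Period imbalance is a minor component, and none at all if the completers split equally between sequences. The handling of two eyes is a related omission but not part of the main finding.

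The effect is confined to one exploratory endpoint with no hypothesis test or decision rule, and the primary slit-lamp estimate does not depend on it. It should be corrected, but it does not threaten the study's main conclusion.

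**What to change.** Make the objective and the analysis agree, by one of two routes.

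1. In section 14.7, add the Test–Control mean difference in 1-week acuity with a two-sided 95% CI. Use a linear mixed model with sequence, period and lens type as fixed effects and a covariance structure that covers both the crossover pairing and the two eyes. A period-adjusted paired analysis of each subject's two-eye average would be equivalent for this purpose. Keep the descriptive table.
2. If description alone is intended, reword the acuity objective in section 2.1 and the synopsis to per-lens estimation.

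Under either route, state how a subject's two eyes are handled in the per-lens intervals.

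The first route costs a paragraph of text and one additional analysis of data already collected at Visits 2 and 5. The second costs wording only. Neither needs new data.
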